14.1.1.5 Decision to proceed with enrollment into Cohort B

A sequential two-stage design will be employed in the Phase II portion of this trial, within each dose level, to evaluate the adverse events of major toxicity (probable or possibly related grade 3 or 4 adverse events including hemorrhage) at end of treatment for potential early termination of the dose in the case of excessive toxicity. After 5 patients have finished 56 days of therapy, the study will be placed on hold and toxicities evaluated. If more than one major toxicity is observed within the first 5 patients enrolled in Cohort A, the cohort will be suspended and detailed toxicity data reviewed for possible closure of the study to further accrual based on DSMC review. The probability of stopping accrual after the first 5 patients based on the true but unknown toxicity event for major hemorrhages is shown in the table below. If the study criteria are met to reopen the second stage, accrual will begin after the first 5 patients have finished study treatment and all toxicity data have been reviewed. With 5 eligible patients in the first stage, the probabilities of observing at least one toxicity with corresponding true rate of 1% and 5% are, respectively, 5% and 23%. With 30 eligible patients the respective probabilities of one or more events are 26% and 79%. The maximum width of a 95% confidence interval on any given toxicity, unadjusted for the two-stage design is 36%. Adjusting for the two-stage design, the maximum 95% confidence interval width would be 50%. If there are greater than 3 major toxicities in the 30 patients in Cohort A, then the cohort will be suspended and detailed toxicity data reviewed for possible closure of the study to further accrual based on DSMC recommendations. If the true but unknown toxicity event for major hemorrhages is 5% and 15%, the probability of proceeding to Cohort B after the evaluation of the 30 patients in Cohort A is 92.5% and 30.8%, respectively. A similar twostage design will be employed for patients enrolled in Cohort B. If there are more than 1 major toxicities in the first 5 patients or three or more

True attributable toxicity	0.05	0.1	0.15	0.2	0.25	0.3	0.35	0.4	0.45
Probability of stopping early after 5 patients	0.023	0.081	0.165	0.263	0.367	0.472	0.572	0.663	0.744
Probability of stopping at the end of the cohort A	0.075	0.373	0.692	0.883	0.964	0.991	0.998	0.999	0.999

major toxicities in the 30 patients in Cohort B, then we will only consider proceeding to the phase III portion of the study with isoquercetin 500 mg daily.

- 14.1.1.6 **Primary endpoint analysis:** D-dimer concentrations will be compared for each patient at day 0 and end of treatment by a paired-t test analysis. Analysis will be performed on an intention to treat basis for patients who undergo randomization and completed the baseline and end of treatment D-dimer assessments.
- 14.1.1.7 Determination of continuation with phase III trial and selection of dose. Following completion of the phase II study, decision will be made by principal investigators whether to proceed with enrollment into the phase III trial. The decision to continue will be principally guided by whether either isoquercetin arm reached the primary endpoint definition. If both isoquercetin arms meet the primary endpoint then selection of dose will be based on degree of reduction in D-dimer levels in each arm relative to baseline and toxicity profile with special attention to major hemorrhage episodes. If neither isoquercetin arm results in significant reduction in d-dimer values relative to baseline, then consideration to advance to phase III will be made based on overall VTE rate in the combined isoquercetin arms. D-dimer is a recognized biomarker of the prothrombotic state but is known to lack specificity in cancer cohorts⁵⁸. Because it is possible that isoquercetin is an effective antithrombotic without altering plasma D-dimer values especially considering potential antiplatelet activity, we will also analyze the cumulative incidence of VTE collectively for the isoquercetin treated patients. A true cumulative incidence VTE rate of less than 10% would be considered promising in the combined isoquercetin arms, whereas a true cumulative incidence rate of 25% would not be worthy of further study. Treatment is considered promising among the 60 patients treated with isoquercetin when nine or fewer VTE are observed. This design has at least a 92% chance of concluding the treatment is effective when the true cumulative incidence

rate is 10%, and less than a 5% chance of concluding the treatment is effective when the true cumulative incidence rate is 25% or more (Fisher exact test). If determination to proceed to phase III is based on promising VTE rates, then the higher dose level of isoquercetin will be utilized.

- 14.1.2 The primary aim of the **phase III trial** is determine whether isoquercetin reduces the cumulative incidence of symptomatic or proximal VTE in cancer patients at 56 days.
 - 14.1.2.1 **Study design:** The trial is a randomized, placebo-controlled, doubleblinded phase III trial. Study subjects are randomized to placebo or isoquercetin. The structure of the study matches the phase II study, the central differences being that VTE is the primary endpoint and a single isoquercetin arm is compared to placebo.
 - 14.1.2.2 **Randomization:** Central randomization (1:1) will be performed by QACT Office at DF/HCC and stratified by cancer diagnosis and institutions.
 - 14.1.2.3 Accrual: Anticipated accrual is 20 patients per month across all sites.

14.1.2.4 Sample size justification:

The overall incidence of thrombosis in cancer populations varies between 2-40% based on histology, stage, chemotherapeutics, additional risk factors and mode of surveillance (imaging or symptomatic events). The overall cumulative incidence of VTE in recently conducted MicroTEC study with similar eligibility criteria and study design was 11.3%. The estimate of isoquercetin benefit is based on data from primary thromboprophylaxis trials that typically achieve VTE rates of 4% or less.^{60,61} Based on the estimated VTE rates of 11% in the placebo and 4% isoquercetin arms, a total of 281 isoquercetin-treated subjects and 281 placebo-treated subjects would be required to reject the null hypothesis that the failure rates for experimental and control subjects are equal with probability (power) 0.85. The 1-sided type I error probability associated with this test of this null hypothesis is 0.025. In order to adjust for death or dropout of 5% prior to 56 days, the sample size is increased by an additional 28 patients. We plan an interim analysis for efficacy or futility after 50% of patients have been randomized that will be guided by O'Brien-Fleming boundaries. This will require an additional increase in sample size of 5% or 28 patients. Therefore, we plan to enroll a total of 618 patients. A total of 30 patients enrolled in the phase II trial will be included in the total accrual target and final VTE endpoint analysis.

14.1.3 Primary endpoint analysis will be performed on an intention to treat basis following randomization for all patients who undergo baseline assessment for the presence of VTE and at least one dose of study medication. The cumulative incidence of VTE

will be assessed by competing risk analysis and differences between arms will be evaluated by the Gray test.^{62,63}

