6.1 Anticipated Toxicities

A list of the adverse events and potential risks associated with the agents administered in this study appear below and will determine whether dose delays and modifications will be made or whether the event requires expedited reporting **in addition** to routine reporting.

A number of clinical trials have shown minimal to no adverse effects from oral quercetin (the parent compound of isoquercetin). In several studies conducted to investigate various potential effects of quercetin on immune function, risk factors for heart disease, or exercise-induced oxidative stress among others, the ingestion of quercetin by healthy subjects (males and females, group sizes ranging from 11 to 63; mean ages for treatment and control groups ranged from 20 to 46 years) at a daily dose of 600 to 1000 mg/day for periods of 1 to 6 weeks was not associated with any reports of adverse effects⁴⁸⁻⁵² A randomized, double-blind, placebo-controlled 12-week study was conducted in which subjects (male and female, ages 18 to 85 years) were randomized to consume a placebo (n = 335) or 500 (n=334) or 1,000 (n=333) mg of quercetin daily. There were no significant toxicities or metabolic changes between the groups.⁵³

Intravenous administration of quercetin can be associated with nephrotoxicity. Doses up to 11.4 mg/kg body weight (equivalent of 694 mg in a 60 kg patient) were associated with transient flushing and mild pain at the injection site⁵⁴. At the higher dose levels of up to 54.1 mg/kg body weight (equivalent to 10,000 mg orally), grade 1-4 nephrotoxicity was described, as well as dyspnea and emesis.

Despite the potential antithrombotic activity of quercetin and flavonoids, hemorrhage has not been described as a toxicity in clinical studies.

The supplied capsules contain ascorbic acid (62 mg) and niacin (5 mg) to prevent oxidation and improve absorption of isoquercetin. The recommended daily allowance of niacin is between 14 and 16 mg. Higher doses of niacin (between 300 mg and 6000 mg daily) are prescribed for hyperlipidemia and can be associated with flushing as well as other side effects such as hepatotoxicity. At physiologic dosing, side effects attributable to niacin would be unexpected. Similarly, ascorbic acid supplementation is not associated with significant toxicity. There are case reports of hemolytic anemia in patients with G6PD deficiency receiving extreme doses (several grams) of ascorbic acid.

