9 STUDY CALENDAR

Baseline evaluations are to be conducted within 15 days prior to start of protocol therapy.

All assessments must be performed prior to administration of any study medication. All study assessments and medications should be administered within \pm 7 days of the protocol-specified date, unless otherwise noted.

Event/Procedure	Screening/ Pre- treatment visit	Day 1 (C1D1)	Day 29 (C2D1)	Day 56 or End of Study Treatment	Survival Assessment
Day Range	-15 to 0		+ 2 days	+ 5 days	Q6 months
History Assessments	Х				
Informed Consent	Х				
Inclusion/Exclusion Criteria	Х				
Medical History	Х		х	х	
ECOG Performance Status Score	х		х	х	
Concomitant medication review	Х		Х	х	
Treatment allocation ⁶	Х				
Dispense study drug		х	Х		
Drug Diary Collection ³			х	х	
Safety Assessments					
Physical examination including vital signs	Х		х	х	
Height and Weight	Х				
AE/SAE assessment	Х		х	х	
Assessment of signs and symptoms of VTE and bleeding	х		х	х	
Laboratory Tests					
Complete blood count with diff	Х	х	х	Х	
РТ/РТТ	Х				
Creatinine	Х		Х		
AST/ALT	Х		Х		
Total bilirubin	Х				
Urine HCG ⁴	Х				
Correlative plasma samples (all sites) ¹		x		х	
Correlative plasma samples (BIDMC only)		X5		х	
Imaging					
Bilateral lower extremity ultrasound				х	
Quality of Life Survey ²		Х		х	

CONFIDENTIAL This document is confidential. Do not disclose or use except as authorized. ¹Correlative lab instructions (TFMP) provided in Appendix E
²QOL survey provided in Appendix D
³Drug Diary
⁴If applicable
⁵Optional correlative labs to be drawn at time 0 and 4 hours (see section 7.1)
⁶Phase II treatment allocation is by sequential dosing cohort, Phase III allocation is by randomization

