14.1 Study Design/Endpoints

- 14.1.1 The primary endpoint of the Phase II trial is to investigate whether isoquercetin significantly reduces d-dimer values in cancer patients. D-dimer is a readily available biomarker used clinically in the prediction and diagnosis of VTE. In cancer cohorts, the D-dimer has modest specificity for predicting symptomatic thrombosis.⁵⁸ However, D-dimer remains the most validated surrogate marker of thrombin generation in vivo and symptomatic VTE.
 - 14.1.1.1 **Study Design**: The trial is a sequential cohort study of isoquercetin 500 mg and 1000 mg daily.
 - 14.1.1.2 Randomization: Patients will not be randomized.
 - 14.1.1.3 Accrual: Anticipated accrual is 10 patients per month across all study sites.

14.1.1.4 Sample Size Justification: Plasma D-dimer levels typically decrease at least 20% following the initiation of anticoagulation.⁵⁹ The sample size is based on a paired t-test of D-dimer concentrations measured on day 1 and end of treatment, to be performed separately for each arm. In the recently completed MicroTEC study, the median baseline D-dimer concentration for all cancer patients enrolled was 815 ug/L.⁴⁷ Based on an estimated standard deviation of 0.3 for the ratio of the D-dimer levels at day 56 over the D-dimer levels at day 1, a total of 26 subjects are needed per arm for a 90% power to declare the reduction significant if the true concentration at end of treatment is reduced by 20% in each isoquercetin arm (one-sided alpha 0.05). Estimated death or dropout of 5% prior to 56 days, the sample size will be increased to a total of total 30 per arm (onesided alpha 0.05). With 30 eligible patients per dose level, there is greater than 60% power to detect an unacceptable attributable grade 3 or 4 rate of 15% at 56 days using a one-sided 10% level exact binomial test in each dose level. (see table below)

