Appendix C:

Cycle 1, Day 1 (Day 1)

I allent ID and Initials . Itospital.
--

Complete blood count with diff

 \Box Platelet count > 90,000/µl

Absolute neutrophil count >1,000/mcL

	~				
1	Corre	lative	nlasma	samp	e
	00110		Prasilia	Sump	

Correlative plasma sample at 0 and 4 hours (BIDMC only, optional)

Quality of life survey

Dispense study drug

Dispense drug diary

Investigator signature:	
Date:	

Cycle 2, Day 1 (Day 29)

Patient ID and Initials:	Hospital:	
	 1	

Physical exam including vital signs

AE/SAE assessment

Assessment of signs and symptoms of VTE and bleeding

Complete blood count with differential, Creatinine, AST/ALT

Absence of grade 3 thrombocytopenia (platelet count > $50,000/\mu$ l)

Non-heme toxicities possibly related to isoquercetin must return to grade 2 or less

Collect signed drug diary and provide a new one

Investigator signature: _____ Date: _____

Day 56 or End of Study treatment

Patient ID and Initials: _____ Hospital: _____

Medical history, ECOG and concomitant medication review

Physical exam including vital signs

AE/SAE assessment

Assessment of signs and symptoms of VTE and bleeding

Complete blood count with differential

Correlative plasma sample

Bilateral lower extremity ultrasound

Quality of Life Survey completed

Collect signed drug diary

Investigator signature: ______ Date: _____

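### Phase II judges grade 3–4 toxicity at 56 days, but no creatinine or AST/ALT is scheduled after Day 29 and no bilirubin or PT/PTT after screening

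*Combined protocol and SAP*

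**What the plan says.** **Endpoint.** Section 14.1.1.5 applies a two-stage rule within each dose level to related grade 3 or 4 adverse events, including hemorrhage, assessed "at end of treatment for potential early termination of the dose in the case of excessive toxicity". The first look follows full treatment: "After 5 patients have finished 56 days of therapy, the study will be placed on hold and toxicities evaluated". Section 14.1.1.4 claims "greater than 60% power to detect an unacceptable attributable grade 3 or 4 rate of 15% at 56 days"; the test named there is exact binomial, one-sided, at the 10% level.

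**Laboratory schedule.** In Section 9:
- Creatinine and AST/ALT are marked at screening and Day 29.
- Total bilirubin and PT/PTT are marked at screening only.
- The blood count with differential is marked at screening, Day 1, Day 29 and the column headed "Day 56 or End of Study Treatment".

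Appendix C agrees. Its Day 29 checklist has "Complete blood count with differential, Creatinine, AST/ALT". Its Day 56 checklist has the blood count and the correlative plasma sample, but no chemistry or coagulation test. Section 9 also requires assessments to precede study medication, so the Day 29 sample comes before cycle 2 dosing.

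**What counts.** Under Section 11.1.1 an abnormal laboratory result is an adverse event only if it causes signs or symptoms, or calls for treatment or further testing.

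**The concern.** The endpoint runs to Day 56, while scheduled renal and transaminase testing stops at Day 29. Bilirubin and PT/PTT have no scheduled on-treatment value at all. A silent abnormality that arises after the last scheduled sample, and that would have led to treatment or further tests had it been seen, is a countable event that the protocol's own tests cannot find.

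The toxicity count helps decide whether Cohort B opens (14.1.1.5) and which dose goes forward (14.1.1.7). Section 14.1.2.1 says phase III follows the phase II structure, so the gap would carry over unless the calendar is amended. The plan treats these tests as relevant elsewhere: Section 3.1.7 uses all four for eligibility, and Appendix A (3.10) counts laboratory tests among the safety parameters.

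**Working it through.** **1. Reproduce the plan's figures.** The Cohort A rule in 14.1.1.5 is to suspend and review if there are 2 or more major toxicities in 5 patients, or 4 or more in 30. The table calls this stopping. With true rate p,

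P(stop) = P(X₅ ≥ 2) + P(X₅ = 0)·P(X₂₅ ≥ 4) + P(X₅ = 1)·P(X₂₅ ≥ 3), each X binomial with rate p.

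At p = 0.15: 0.1648 + 0.4437 × 0.5289 + 0.3915 × 0.7463 = 0.692.

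| True rate | After 5: computed / stated | Whole cohort: computed / stated |
|---|---|---|
| 0.05 | 0.0226 / 0.023 | 0.0749 / 0.075 |
| 0.10 | 0.0815 / 0.081 | 0.3729 / 0.373 |
| 0.15 | 0.1648 / 0.165 | 0.6916 / 0.692 |
| 0.20 | 0.2627 / 0.263 | 0.8831 / 0.883 |

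All agree within 0.001. The power claim also reproduces: a single-stage test that rejects at 4 or more of 30 has power 0.678 at 15%. Its size is 0.061 at a null rate of 5%. The plan does not state the null; 5% is assumed here. All these figures treat every qualifying event to Day 56 as detected.

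**2. Set endpoint against schedule.**

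| Test | Last scheduled value | Treatment time after it |
|---|---|---|
| Blood count | Day 56 | none |
| Creatinine, AST/ALT | Day 29 | 56 − 29 = 27 of 56 days (48%) |
| Total bilirubin, PT/PTT | Screening | all 56 days |

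**3. Illustrate the effect of missed events.** The documents do not say what share of qualifying events would show only on chemistry. Call it s, and assume that events are uniform over 56 days, that all events up to Day 29 are seen, and that no chemistry-only event after Day 29 is seen. The visible rate is then 0.15 × (1 − s × 27/56), which goes into the formula in step 1.

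| Assumed s | Visible rate | P(stop Cohort A) |
|---|---|---|
| 0 | 0.150 | 0.69 |
| 5% | 0.146 | 0.67 |
| 10% | 0.143 | 0.65 |
| 25% | 0.132 | 0.59 |
| 50% | 0.114 | 0.47 |

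These are neither estimates nor bounds. The loss would be larger if toxicity builds with exposure, or if bilirubin or coagulation events before Day 29 are also missed. It would be smaller if local blood tests find some events.

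**The case against.** The case against giving this much weight is substantial.

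- **Much toxicity is still seen.** The blood count is repeated at Day 56. History, physical examination and adverse-event assessment at that visit can find symptomatic events. Section 11.2 accepts events found by any laboratory test, so local chemotherapy bloods may reveal others. This stands. It limits the gap to silent renal, hepatic and coagulation changes, although the protocol neither schedules nor requires the local tests.
- **Section 11.1.1 narrows what counts.** A silent value that needs no action is not an adverse event. This stands. What remains is values that would have prompted treatment or testing; a test that is never done cannot prompt either.
- **Section 6.1 gives little reason to expect these events.** It says that "administration of quercetin can be associated with nephrotoxicity", but of intravenous use, with grade 1–4 nephrotoxicity at levels it equates to 10,000 mg orally. Hepatotoxicity is linked to niacin at 300 to 6000 mg daily; the capsules give 2 × 5 = 10 mg or 4 × 5 = 20 mg. Section 6.1 also reports a 12-week randomized study of quercetin at up to 1,000 mg daily without significant toxicity, and the expected-event list in 6.1.1 has no renal or hepatic item. This stands, and argues for a small s. At 5% or 10% the probability of stopping stays above the 60% quoted in 14.1.1.4.
- **Any such rule acts on observed toxicity.** Imperfect ascertainment qualifies the table without making it wrong. This also stands.

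A reader might infer that laboratory toxicity in the second half of treatment goes largely unseen, or that 48% of toxic events are lost. The documents support neither: the 48% is time without scheduled chemistry, not a share of events, and hematologic toxicity is measured throughout.

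**Conclusion.** The point holds as a limited mismatch between a 56-day toxicity endpoint and a laboratory schedule that ends earlier. It affects silent renal and transaminase abnormalities after the Day 29 sample, and silent bilirubin and PT/PTT abnormalities throughout treatment, where they would have required treatment or further testing. The schedule facts are firm: where the calendar and the checklists cover the same visit they agree, and no other section schedules these tests later.

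The size is not known. The fall from 0.69 to between 0.67 and 0.47 rests on an assumed chemistry-only share of 5% to 50%, uniform timing and a true rate of 15%. It should not be read as a forecast, nor as a worst case. The stopping table is not in error; it carries an unstated assumption of full detection. This is a worthwhile, inexpensive improvement to safety ascertainment, and not a flaw that invalidates the phase II decisions.

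**What to change.** Reconcile Section 9 and the Appendix C Day 56 checklist with the endpoint in 14.1.1.4–14.1.1.5. Add creatinine, AST/ALT and total bilirubin to the existing end-of-treatment blood draw, and PT/PTT if coagulation toxicity is to be counted.

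If the schedule is kept, say three things in 14.1.1.4–14.1.1.5: protocol assessment of renal and transaminase laboratory toxicity ends at Day 29; bilirubin and PT/PTT are not assessed on treatment; and the stopping table assumes full detection to Day 56.

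The cost of the first option is one routine panel per patient, about 2 × 30 = 60 in phase II, at a visit where blood is already drawn, plus an amendment to the calendar and checklist. No new visit is needed. A single Day 56 sample would still miss changes that appear and resolve between Day 29 and Day 56, so it narrows the gap without closing it. The second option costs only a text change.

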5 TREATMENT PLAN

Treatment will be administered on an outpatient basis. Expected toxicities and potential risks as well as dose modifications for isoquercetin are described in Section 6 (Expected Toxicities and Dosing Delays/Dose Modification).

Phase	Agent*	Isoquercetin Dose	Route	Schedule	Cycle
Phase II	Isoquercetin (IQC- 950AN) 250mg	Cohort A: 500 mg or Cohort B: 1000 mg	Oral capsules	Cohort A: 2 capsules once daily Cohort B: 4 capsules once daily	28 days
Phase III	Isoquercetin (IQC- 950AN) or Placebo	Cohort C: TBD or Cohort D: Placebo	Oral capsules	Once daily (TBD)	28 days

*All capsules (placebo and isoquercetin) include ascorbic acid 62 mg and niacin 5 mg.

Phase II

Cohort A: Patients will receive isoquercetin 500 mg once daily (2 capsules). Continued enrollment into the dosing cohort will be based on the safety evaluation of the initial 5 patients. If there are ≥ 1 grade 3 or 4 toxicity (possibly, probably or definitely related to isoquercetin), then decision to enroll an additional cohort of 25 patients will be based on DSMC recommendations. If there are ≥ 3 grade 3 or 4 adverse events (possibly, probably or definitely related to isoquercetin), the decision to proceed with enrollment into cohort B will be based on PSMC.

Cohort B: Patients will receive isoquercetin 1000 mg once daily (4 capsules). Similar to cohort A, continued enrollment will be based on the absence of attributable significant toxicities.

For both cohorts A and B, lower extremity ultrasound will be performed at end of treatment visit. Baseline D-dimer and correlative labs will be drawn at Day 1 and at end of treatment visit. Patients will be followed for survival after completion of end of treatment visit.

Phase III

Following the completion of the phase II portion, enrolled patients will be randomized 1:1 to Arm C (isoquercetin) or Arm D (placebo). The dose for Arm C will be determined after evaluation of the Phase II portion of the trial. The protocol will be amended when the decision is made whether to proceed to Phase III and what dose to use for Arm C. The study will be double-blinded to treatment arm. Lower extremity ultrasound will be performed at end of treatment. Baseline D-dimer and correlative labs will be drawn at Day 1 and at end of treatment. Patients will be followed for survival after completion of end of treatment assessment.

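### Cohort B's limit of three or more toxicities in 30 does not fit the claimed 10% test level if the null rate is 5%, and Sections 5 and 14.1.1.5 differ on exactly 3 of 30 in Cohort A

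*Combined protocol and SAP*

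**What the plan says.** **Level and power.** Section 14.1.1.4 states that 30 patients per dose give "greater than 60% power to detect an unacceptable attributable grade 3 or 4 rate of 15% at 56 days". It describes the method behind that figure as "using a one-sided 10% level exact binomial test in each dose level" and refers to the table that follows. No null rate is given.

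**Cohort A, Section 14.1.1.5.** At the first look: "If more than one major toxicity is observed within the first 5 patients enrolled in Cohort A, the cohort will be suspended". At the end, more than 3 of 30 suspends the cohort for DSMC review. Whatever the first count, after 5 patients finish "the study will be placed on hold and toxicities evaluated". The chance of proceeding to Cohort B is given as 92.5% at a true rate of 5% and 30.8% at 15%. The table's cumulative row is labelled for Cohort A.

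**Cohort B, Section 14.1.1.5.** The design is called similar. More than 1 of the first 5, or three or more of 30, means phase III is considered only with 500 mg.

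**Section 5.** For Cohort A the first trigger is worded "If there are ≥ 1 grade 3 or 4 toxicity (possibly, probably or definitely related to isoquercetin"). Its consequence, when it is met after the initial 5 patients, is "then decision to enroll an additional cohort of 25 patients will be based on DSMC recommendations". A second trigger comes next: "If there are ≥ 3 grade 3 or 4 adverse events". When those events are at least possibly related to the drug, "the decision to proceed with enrollment into cohort B will be based on PSMC". The second trigger has no denominator and its committee acronym differs from the first. For Cohort B, Section 5 says only that enrolment continues if no significant attributable toxicity is seen.

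**The concern.** There are two separate points.

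First, the 10% level is claimed for both doses, but the two doses have different final limits. The claim can be checked against Cohort A's limit. Cohort B's limit is one event lower, so its chance of being crossed at a low toxicity rate is higher, and that chance is printed nowhere. The limit matters because crossing it removes 1000 mg from consideration for phase III.

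Second, Section 5 and 14.1.1.5 do not give the same instruction when Cohort A ends with exactly 3 toxicities in 30. One lets Cohort B open; the other calls for a committee decision first. The printed operating characteristics describe only the former.

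**Working it through.** **Inputs.** 5 + 25 patients and the limits above (Sections 5 and 14.1.1.5); level 10%, unacceptable rate 15% and power above 60% (14.1.1.4). Each patient counts at most once. X1 ~ Bin(5, p), X2 ~ Bin(25, p).

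**Step 1: reproduce the printed Cohort A figures.** Proceeding needs X1 ≤ 1 and X1 + X2 ≤ 3:

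P(proceed) = P(X1=0)·P(X2≤3) + P(X1=1)·P(X2≤2)

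- 5%: 0.7738 × 0.9659 + 0.2036 × 0.8729 = 0.925, so stopping is 0.075
- 10%: 0.5905 × 0.7636 + 0.3280 × 0.5371 = 0.627, so stopping is 0.373
- 15%: 0.4437 × 0.4711 + 0.3915 × 0.2537 = 0.308, so stopping is 0.692

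These are the printed row and the stated 92.5% and 30.8%. The first-look row is P(X1 ≥ 2) = 0.0226, 0.0815 and 0.1648, also as printed. So the table describes more than 1 of 5, then more than 3 of 30.

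**Step 2: the same calculation for Cohort B** (X1 ≤ 1 and X1 + X2 ≤ 2):

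P(limit not crossed) = P(X1=0)·P(X2≤2) + P(X1=1)·P(X2≤1)

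- 5%: 0.7738 × 0.8729 + 0.2036 × 0.6424 = 0.806, so crossing is 0.194
- 10%: 0.5905 × 0.5371 + 0.3280 × 0.2712 = 0.406, so crossing is 0.594
- 15%: 0.4437 × 0.2537 + 0.3915 × 0.0931 = 0.149, so crossing is 0.851

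From 20% to 45% the values are 0.957, 0.990, 0.998, then above 0.999 three times. The first-look row serves both cohorts; the cumulative row does not.

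**Step 3: test level.** The documents name no null, so a range is shown. Single stage, X ~ Bin(30, p):

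| Rate | P(X ≥ 3), Cohort B limit | P(X ≥ 4), Cohort A limit |
|---|---|---|
| 3% | 0.060 | 0.012 |
| 4% | 0.117 | 0.031 |
| 5% | 0.188 | 0.061 |
| 6% | 0.268 | 0.103 |
| 15% (power) | 0.849 | 0.678 |

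The level reaches 0.10 at a null of 3.7% for three or more (the same to one decimal, 0.0365, with the two-stage rule) and at 5.9% for four or more (0.0559 with the two-stage rule).

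A 5% null is inferred for three reasons. It is the lowest rate in the table. Section 14.1.1.5 pairs it with 15%. And at a 5% null the smallest cut-off with level at most 10% is four or more of 30, whose power at 15% is 0.678, in line with the stated figure of above 60%.

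**Step 4: exactly 3 of 30 in Cohort A.** The chance of ending there without a first-look suspension is the difference between Steps 2 and 1:

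- 5%: 0.1938 − 0.0749 = 0.119
- 10%: 0.5939 − 0.3729 = 0.221
- 15%: 0.8510 − 0.6916 = 0.159 (from unrounded values)

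This reads Section 5's three or more as out of 30. That is the natural reading, because the sentence governs entry to Cohort B and follows the one on enrolling 25 more.

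**The case against.** **A stricter Cohort B limit may be deliberate.** A tighter limit on the doubled dose is cautious, and similar need not mean identical. This stands: nothing shows that three or more is an error. A reader might infer that the limit must be relaxed, and the documents do not support that. What remains is that the claimed level and the printed row were not adapted to it.

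**The null is not stated.** This also stands. A reader might infer that the Cohort B limit simply fails a 10% test. That holds only for nulls above about 3.7%, and 14.1.1.4 could be read as a general statement about 30 patients. But it says the test applies at each dose level and points to the table, whose lowest rate is 5%. The power statement is not in doubt: both limits exceed 60%.

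**The first-look wordings can coexist.** A reader might infer from at least 1 versus more than 1 of 5 that the sections conflict outright, or that patients could be enrolled without review. They do not support that. The consequences differ (committee recommendation versus suspension), so the wordings can be read as tiers, and 14.1.1.5 holds the study and requires review of the toxicity data after 5 patients in any case. The tiers are not written down, but the operational effect is small.

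**Three of 30 leads to a decision, not a refusal.** Treating every such case as not proceeding would cut the chance of opening Cohort B at 5% from 0.925 to 0.806. Section 5 does not say the committee would refuse, so that is a bound and not the effect of the discrepancy.

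**Conclusion.** The point holds, as something to correct before the cohorts are evaluated.

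For Cohort B, the claimed 10% level does not match the limit of three or more of 30 if the null is 5%. The level is then 0.188 single-stage, or 0.194 with the first look, against 0.061 and 0.075 for Cohort A's limit. Power at 15% is 0.849 single-stage. The mismatch depends on the inferred null and disappears at about 3.7% or below. That the null is unstated and the cumulative row does not cover Cohort B needs no assumption.

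For Cohort A, the sections differ in substance for one count, exactly 3 of 30, with chance 0.119, 0.221 and 0.159 at 5%, 10% and 15%. This assumes the denominator is 30. The consequence is an ambiguous threshold for opening Cohort B.

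**What to change.** **Cohort A.** State one rule in Sections 5 and 14.1.1.5: more than 1 of 5 and more than 3 of 30, which is what the table describes. Alternatively, write the tiers out: committee decision at 1 of 5 or 3 of 30, suspension above those counts. If tiers are kept, give the denominator and replace PSMC with DSMC, the committee that 12.2 names for phase II. Bring Section 5's Cohort B sentence into line with its numerical limits, and check that 12.2's wording on DSMB review after an enrolment hold agrees.

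**Cohort B.** State the null rate, then choose one of:

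- Keep three or more of 30. Add its cumulative row for true rates 0.05 to 0.45 (0.194, 0.594, 0.851, 0.957, 0.990, 0.998, >0.999, >0.999, >0.999) and correct the level in 14.1.1.4 for this dose (0.188 single-stage at a 5% null).
- If three or more was a slip for more than 3, correct it and label the existing row for both cohorts.

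**Cost.** Wording changes and at most one table row, with no extra patients or procedures. The second option has a safety cost: the chance of ruling out 1000 mg at a true rate of 15% falls from 0.851 to 0.692. Keeping the limit and restating its figures is therefore the low-cost default. The choice of threshold belongs to the investigators and the DSMC.
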